7.2 Medical History

Medical history data will be coded using the Medical Dictionary for Regulatory Activities (MedDRA). The actual version of the MedDRA coding dictionary will be noted in the statistical tables and clinical study report. The number and percentage of subjects in each medical history category (by MedDRA system organ class and preferred term) will be summarized. The system organ class (SOC) will be presented in alphabetical order, and the preferred terms will be presented in alphabetical order within each SOC. Subjects reporting more than one condition/diagnosis will be counted only once in each row (SOC or preferred term). Migraine history will be summarized separately according to eCRF.

7.3 Prior and Concomitant Medications

Prior and concomitant medications will be summarized separately by generic name. The number and percentage of subjects taking prior and concomitant medications will be summarized by generic name. Concomitant medication will be summarized for each open-label period and overall. A prior medication is defined as any medication taken prior to the date of the first dose of study drug.

A concomitant medication in the open-label atogepant treatment period (Period 1) is defined as any medication that started prior to the date of the first dose of study drug and continue to be taken after the first dose of study drug or any medication that started on or after the date of the first dose of study drug, but not after the date of the last dose of study drug in Period 1 plus 30 days (if subject discontinued from study drug in Period 1) or Visit 5 whichever comes later.

A concomitant medication in the open-label atogepant + ubrogepant treatment period (Period 2) is defined as any medication that started prior to the date of the first dose of study drug in Period 2 and continue to be taken after the first dose of study drug in Period 2 or any medication that started on or after the date of the first dose of study drug in Period 2, but not after the date of the last dose of study drug plus 30 days or Visit 9 whichever comes later.

The number and percentage of subjects taking medications will be summarized by generic drug name based on the World Health Organization (WHO) Drug Dictionary Enhanced for both prior and concomitant medications.

8.0 Handling of Potential Intercurrent Events for the Primary and Secondary Endpoints

The efficacy endpoints are exploratory, so no handling of intercurrent events for efficacy endpoints will be provided.

9.0 Efficacy Analyses

9.1 General Considerations

All efficacy analyses will be conducted in the mITT 1 or mITT 2 Population.

9.2 Handling of Missing Data

Descriptive statistics for efficacy endpoints will be based on observed cases (OC) only. Missing data will be handled using mixed model for repeated measures (MMRM) without imputation for the efficacy analysis for continuous endpoints unless specified otherwise.

9.3 Exploratory Efficacy Endpoint(s) and Analyses

9.3.1 Exploratory Efficacy Endpoint(s)

The exploratory efficacy endpoints are listed in Section 3.2.

9.3.2 Analysis of Exploratory Efficacy Endpoints

Continuous Endpoints

The change from baseline in mean monthly migraine days, headache days, and acute medication use days across Weeks 1 to 12, Weeks 13 to 24, and at each 4-week interval will be analyzed using a mixed-effect model for repeated measures (MMRM) for each period (open-label atogepant period or open-label atogepant + ubrogepant period), including visit as a categorical fixed effect, and baseline value and baseline-by-visit interaction as covariates. An unstructured covariance matrix will be used to model the covariance of within-subject repeated measurements. The Kenward-Roger approximation will be used to estimate the denominator degrees of freedom. The analysis will be performed based on postbaseline values using only the observed cases without imputation of missing values. Contrasts will be constructed to obtain the average treatment effects across the 12-week period for Weeks 1 to 12 or Weeks 13 to 24. The treatment effect (across the 12-week period for Weeks 1 to 12 or Weeks 13 to 24, and at each 4-week

interval) will be estimated by the least square (LS) Means, the standard error (SE) and 95% confidence intervals.

(HIT)-6 total score is derived as specified in the Appendix A. The change from baseline for (HIT)-6 total score will be analyzed similarly as above using MMRM.

The percent work time missed, percent impairment while working, percent overall impairment, and percent activity impairment due to migraine at Weeks 4, 8, 12, 16, 20, and 24 as assessed by the Work Productivity and Activity Impairment Questionnaire: Migraine (WPAI:MIGRAINE) are derived as specified in Appendix A. The change from baseline for these endpoints will be analyzed similarly as above using MMRM.

MSQ Role Function-Preventive domain score, Role Function-Restrictive domain score and Emotional Function domain score are derived as specified in Appendix A. The change from baseline for these endpoints will be analyzed similarly as above using MMRM.

(PHQ)-4 score is derived as specified in Appendix A. The change from baseline for (PHQ)-4 will be analyzed similarly as above using MMRM.

The MTOQ-6 score is derived as specified in Appendix A. The MTOQ-6 score will be summarized by visit.

Percentages of migraine attacks treated with ubrogepant that result in pain freedom at 2 hours, pain relief at 2 hours, sustained pain freedom from 2 to 24 hours, and sustained pain relief from 2 to 24 hours across Weeks 13 to 24 and at each 4-week interval will be summarized using descriptive statistics.

Binary or Categorical Endpoints

The responders are defined as subjects with at least 25%, 50%, 75%, and 100% reduction compared to baseline in mean monthly migraine days across Weeks 1 to 12, Weeks 13 to 24, and at each 4-week interval. They will be summarized using descriptive statistics.

Patient satisfaction with atogepant, ubrogepant, and concomitant use of atogepant and ubrogepant are categorized as extremely satisfied, satisfied, slightly satisfied, neither satisfied nor dissatisfied, slightly dissatisfied, dissatisfied, and extremely dissatisfied. The proportions of patient satisfaction responders, defined as subjects who are satisfied or extremely satisfied with the study treatment for migraine prevention, will be summarized using descriptive statistics by visits.

Proportions of subjects with at least a 5-point improvement (decrease) from baseline in HIT-6 total score at Weeks 4, 8, 12, 16, 20, and 24 will be summarized using descriptive statistics.

Proportions of subjects with PGIC of "much better" or "very much better" at Week 12 (atogepant) and Week 24 (atogepant + ubrogepant) will be summarized.

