1.0 Introduction

This Statistical Analysis Plan (SAP) describes the statistical analyses for atogepant Study M23-072, A Phase 4, Multicenter, Open-Label Study to Evaluate the Safety, Tolerability, and Efficacy of the Concomitant Use of Ubrogepant for the Acute Treatment of Migraine in Subjects Taking Atogepant for the Preventive Treatment of Episodic Migraine.

Study M23-072 is to evaluate the safety and tolerability of the concomitant use of ubrogepant 100 mg for the acute treatment of breakthrough migraine headache in subjects taking atogepant 60 mg once daily for preventive treatment of EM.

The SAP will not be updated in case of administrative changes or amendments to the protocol unless the changes impact the analysis.

Unless noted otherwise, all analyses will be performed using SAS Version 9.4 (SAS Institute Inc., Cary, NC 27513) or later under the LINUX operating system.

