2.0 Study Design and Objectives

2.1 Objectives, Hypotheses and Estimands

The primary objective of this study is to evaluate the safety and tolerability of the concomitant use of ubrogepant 100 mg for the acute treatment of breakthrough migraine headache in subjects taking atogepant 60 mg once daily for preventive treatment of EM.

The exploratory objectives are:

- To evaluate the clinical benefit of the concomitant use of ubrogepant 100 mg, taken as needed, and atogepant 60 mg once daily in subjects with EM.
- To explore the efficacy of ubrogepant 100 mg, taken as needed, for the acute treatment of migraine in subjects taking atogepant 60 mg once daily for preventive treatment of EM.

The efficacy endpoints are exploratory in this study; therefore, no estimand attributes for efficacy endpoints will be provided.

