2.3 Treatment Assignment and Blinding

Approximately 235 subjects will be enrolled to receive the following open-label treatment:

- Open-label atogepant treatment period: atogepant 60 mg once daily for 12 weeks (Day 1 to Week 12)
- Open-label atogepant and ubrogepant concomitant use treatment period: atogepant 60 mg once daily + ubrogepant 100 mg as needed to treat breakthrough migraine headache for 12 weeks (Week 12 to 24)

No randomization or stratification is required as this will be an open-label study.

All subjects will be assigned a unique identification number by the IRT at the Screening Visit. For subjects who rescreen, the screening number assigned by the IRT at the initial Screening Visit should be used.

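### The one-arm MMRM intervals for mean change are conditional on the observed baseline mean; read as intervals for the population mean change, they are too narrow by an amount the documents do not fix

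*SAP*

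**What the plan says.** The study has one arm: SAP 2.3 states "No randomization or stratification is required as this will be an open-label study", and protocol 4.2 gives the choice of control group as not applicable.

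For change in migraine days, headache days and acute medication use days, SAP 9.3.2 fits one MMRM per treatment period, "including visit as a categorical fixed effect, and baseline value and baseline-by-visit interaction as covariates". It adds "An unstructured covariance matrix will be used to model the covariance of within-subject repeated measurements" and "The Kenward-Roger approximation will be used to estimate the denominator degrees of freedom". The result, which the SAP labels a treatment effect, "will be estimated by the least square (LS) Means, the standard error (SE) and 95% confidence intervals", at each 4-week interval and for the 12-week average: "Contrasts will be constructed to obtain the average treatment effects across the 12-week period for Weeks 1 to 12 or Weeks 13 to 24". HIT-6, WPAI, MSQ and PHQ-4 are to be analysed in a similar way. Protocol 7.4 gives the same model.

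Neither document says at which baseline value the LS means are evaluated, or whether the intervals are conditional on the observed baselines. The target is also left open; SAP 2.1 says "The efficacy endpoints are exploratory in this study; therefore, no estimand attributes for efficacy endpoints will be provided".

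**The concern.** In a randomised two-arm trial this model is routine. Both arms' LS means are evaluated at the same baseline value, so the sampling error of that value cancels in the treatment difference. Here there is no difference to take. The LS mean is the result, and its model-based SE treats the baseline mean as a fixed constant. Another sample of subjects would have another baseline mean, and the mean change would move with it in proportion to the slope of change on baseline. The SE leaves that movement out. Kenward-Roger does not restore it, because it also works conditionally on the covariates.

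The SAP calls the result a treatment effect and defines no estimand, so most readers will take the interval as describing mean change in the population sampled. The same model serves all seven outcome groups. It also serves the interim analysis at 30 or more Visit 8 completers, which is meant to support reimbursement negotiations (protocol 7.6, SAP 11.0). Protocol 7.4 further announces nominal p-values; if any were reported for mean change, they would rest on the same SE.

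**Working it through.** **The plan's own figures.** The documents state precision only for AE rates. 235 × (1 - 0.15) = 199.75, matching the stated 200 or so. The 95% half-width 1.96 × sqrt(p(1-p)/n) at n = 200 is 3.02% for p = 5% and 4.95% for p = 15%, matching the stated 3% to 5%. No SE or width is stated for any MMRM LS mean.

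**Inputs.** From the documents: one arm, the model terms, LS means with 95% CIs, n of about 235 and 200, and an interim with at least 30 completers. Assumed: LS means evaluated at the observed baseline mean. Not given: any SD, or any correlation between baseline and later values.

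**Formula (complete data).** Let b be the slope of change on baseline, s_x the baseline SD and s_res the residual SD.

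- Model variance of the LS mean: s_res^2/n
- Sampling variance of the mean change: (s_res^2 + b^2·s_x^2)/n
- Ratio of SEs: sqrt(1 - r^2), with r the correlation of change with baseline
- Coverage of a nominal 95% interval: 2Φ(1.96·sqrt(1 - r^2)) - 1

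| \|r\| | SE ratio | CI too short by | Coverage |
|---|---|---|---|
| 0 | 1.000 | 0% | 95.0% |
| 0.2 | 0.980 | 2.0% | 94.5% |
| 0.3 | 0.954 | 4.6% | 93.8% |
| 0.4 | 0.917 | 8.3% | 92.8% |
| 0.5 | 0.866 | 13.4% | 91.0% |
| 0.6 | 0.800 | 20.0% | 88.3% |
| 0.7 | 0.714 | 28.6% | 83.8% |

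**What r might be.** Let k be the post-baseline SD divided by the baseline SD, and ρ the pre-post correlation. Then r^2 = (ρk - 1)^2/(k^2 + 1 - 2ρk). With k = 1 and ρ = 0.5, r^2 = 0.25/1 = 0.25, so |r| = 0.5. With k = 1.5 and ρ = 0.7, r^2 = 0.0025/1.15 = 0.002, and coverage is 95.0%. A wider post-baseline spread is possible, because eligibility confines baseline to 4 to 14 migraine days (protocol 5.1).

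**12-week average.** The same formula holds, with r for the averaged change. A simulation of the three-visit model, with complete data and 10,000 runs per setting, assumed equal SDs of 2.9 (a uniform spread over 4 to 14 days gives 10/sqrt(12) = 2.9) and correlation 0.7 between post-baseline visits.

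| n | Coverage at ρ = 0.3 | ρ = 0.5 | ρ = 0.7 |
|---|---|---|---|
| 200 | 86.4% | 89.8% | 91.7% |
| 30 | 87.3% | 90.1% | 91.6% |

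The shortfall does not shrink with n. With dropout missing at random and n = 235 (1,500 runs per setting), coverage was 87.8%, 89.7% and 90.4%.

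**Two checks.** Adding b^2·s_x^2/n to the squared SE brought coverage of the 12-week average to 94.8%-95.5% with complete data (n = 235, 200 and 30) and 94.4%-94.6% with dropout. With the target redefined as mean change at the observed baseline mean, the planned interval covered 94.7%-95.2%.

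**In days.** With SD 2.9 and ρ = 0.5, the SD of change at one visit is 2.9 × sqrt(2 - 2 × 0.5) = 2.9.

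- n = 200: the full half-width is 1.96 × 2.9/sqrt(200) = 0.40 days, and the planned one is 0.866 × 0.40 = 0.35.
- n = 30: 1.96 × 2.9/sqrt(30) = 1.04 days, against 0.866 × 1.04 = 0.90.

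**The case against.** The strongest reply is that the intervals are not wrong in themselves. A covariate-adjusted LS mean estimates the mean change at a given baseline, and for that target the coverage is nominal. The documents decline to define an estimand, so they do not contradict this reading. That stands. But the SAP does not state the conditional reading either, and the treatment-effect label invites the other one.

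A reader might infer three stronger things that the documents do not support.

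- *That every continuous efficacy interval is affected.* SAP 9.4 plans its ubrogepant-use subgroup intervals as plain summary statistics, which include baseline variation. Those intervals escape the problem, although for that reason they are not directly comparable with the MMRM intervals for the same variables.
- *That coverage is in the 80s.* This needs a large |r|, and no outcome's r is given. At |r| of 0.2 or less the effect is close to nil, and r may differ between outcomes.
- *That the study's conclusions are at risk.* The primary objective is safety, the sample size rests on AE precision, and the efficacy endpoints are exploratory with no success threshold. Under the assumptions above the absolute difference at n = 200 is about 0.05 days. The lack of a control group limits interpretation of mean change more than this does.

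The evaluation point of the LS means is also an assumption, though the ordinary one.

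**Conclusion.** The point holds in limited form. Conditional on the observed baseline mean, the intervals in SAP 9.3.2 and protocol 7.4 are valid. As intervals for mean change in the population sampled, they are too narrow by sqrt(1 - r^2), where r belongs to the visit or 12-week average in question. Without r the size is only a range, from no effect at r = 0 to 83.8% coverage at |r| = 0.7. The conclusion rests on LS means being evaluated at the observed baseline mean. It covers the MMRM intervals for migraine, headache and acute medication use days, HIT-6, WPAI, MSQ and PHQ-4. It is worth correcting because the intervals will be read unconditionally and the correction is cheap. It does not touch the point estimates or the primary safety analysis.

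**What to change.** Preferred: put baseline into the response vector as time 0, with an unstructured covariance over baseline and the post-baseline visits of the period, and report visit-minus-baseline contrasts and their 12-week averages. This keeps the likelihood-based handling of missing data.

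Alternative: keep the planned model, state that LS means are evaluated at the observed baseline mean, and add b^2·s_x^2/n to the squared SE. Here b is the slope of change on baseline for the visit concerned, or the averaged slope for a 12-week mean.

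Either change should be made before the interim and entered in SAP Appendix F, which now reports no changes from the protocol-planned analyses. The cost is a few lines of SAP text and model code, no new data, and somewhat wider intervals: 1/0.866 = 1.155 times as wide at |r| = 0.5.

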9.4 Efficacy Subgroup Analyses

For the efficacy endpoint, change from baseline in mean monthly migraine days, headache days, and acute medication use days, subgroup analyses will be performed by ubrogepant usage subgroups.

Two subgroups will be applied in subgroup analyses for subjects who took ubrogepant:

Subgroups by number of ubrogepant use days:

- Never used ubrogepant
- Low ubrogepant use: 1-3 days of ubrogepant taken in the atogepant + ubrogepant treatment period
- Moderate ubrogepant use: 4-9 days of ubrogepant taken in the atogepant + ubrogepant treatment period
- High ubrogepant use: ≥ 10 days of ubrogepant taken in the atogepant + ubrogepant treatment period

Subgroup by number of ubrogepant doses taken:

- Never used ubrogepant
- Low ubrogepant use: 1-6 doses of ubrogepant taken in the atogepant + ubrogepant treatment period
- Moderate ubrogepant use: 7-18 doses of ubrogepant taken in the atogepant + ubrogepant treatment period
- High ubrogepant use: 19+ doses of ubrogepant taken in the atogepant + ubrogepant treatment period

For each subgroup analysis, summary statistics will be provided, including mean and standard deviation, minimum, maximum, and 95% CI for baseline and change from baseline across Weeks 13-24.

10.0 Safety Analyses

10.1 General Considerations

The safety analyses will be performed using the Safety Population 1 or 2. The safety endpoints include AEs, clinical laboratory evaluations, vital sign measurements, ECG parameters, the C-SSRS, and pregnancy test. For each of the clinical laboratory, vital sign, and ECG parameters, the last non-missing safety assessment before the first dose of study drug will be used as the baseline for all analyses of that safety parameter.

Continuous variables will be summarized by the number of subjects, mean, standard deviation (SD), median, Q1, Q3, minimum, and maximum values. Categorical variables will be summarized by number and percentage of subjects.

10.2 Adverse Events

Adverse events (AEs) will be summarized and presented using primary MedDRA System Organ Class (SOCs) and preferred terms (PTs) according to the version of MedDRA coding dictionary used for the study at the time of database lock. The actual version of the MedDRA coding dictionary used will be noted in the AE tables and in the clinical study

report. Specific adverse events will be counted once for each subject for calculating percentages, unless stated otherwise. In addition, if the same adverse event occurs multiple times within a subject, the highest severity and level of relationship to investigational products will be reported.

10.2.1 Treatment-Emergent Adverse Events

Treatment-emergent AEs are defined as any AE with the onset that is after the first dose of study drug. Events when the onset date is the same as the study drug start date are assumed to be treatment-emergent. An AE that occurs more than 30 days after the last dose of open-label study treatment or Visit 8 whichever comes later will not be counted as a TEAE.

The number and percentage of subjects experiencing treatment-emergent AEs will be summarized by the open-label atogepant treatment period, the open-label concomitant atogepant + ubrogepant treatment period, and the entire treatment period.

TEAEs that started after the date of last dose of study treatment will be considered as newly emergent. The number and percentage of subjects reporting newly emergent TEAEs will be summarized by system organ class and preferred term.

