2.4 Sample Size Determination

Approximately 235 subjects will be assigned to receive open-label atogepant 60 mg once daily for the preventive treatment of episodic migraine at Baseline/Visit 2 (Day 1). Based on historical data from previously completed clinical studies, it is assumed that 15% of subjects will discontinue from the study during the atogepant treatment period (Day 1 to Week 12). Therefore, approximately 200 subjects will be assigned to also receive ubrogepant 100 mg for the acute treatment of migraine starting at Visit 5 (Week 12).

This sample size will provide estimation for AEs of interest occurring in either the open-label atogepant treatment period (Day 1 to Week 12) or the open-label atogepant and ubrogepant concomitant use treatment period (Weeks 12 to 24) with a precision (defined as the half width of 95% confidence interval) of approximately $\pm 3\%$ to 5%.

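### SAP 10.2.1 does not say which period's TEAE column receives post-treatment events, so the two period percentages may rest on unequal windows and in any case describe different subjects

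*SAP*

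**What the plan says.** SAP 10.2.1 has one TEAE window for the whole study. It opens at the first dose, and the event excluded at the other end is: "An AE that occurs more than 30 days after the last dose of open-label study treatment or Visit 8 whichever comes later". The number and percentage of subjects with TEAEs are to be "summarized by the open-label atogepant treatment period, the open-label concomitant atogepant + ubrogepant treatment period, and the entire treatment period". The section contains no rule assigning an event to a period.

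On events after treatment it adds: "TEAEs that started after the date of last dose of study treatment will be considered as newly emergent". These are tabulated by system organ class and preferred term. They remain TEAEs, and the SAP does not say whether they also stay in the period columns.

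Explicit period windows exist only for concomitant medication (SAP 7.3). For a subject who continues, Period 1 closes at Visit 5. For a subject who stops in Period 1, it closes at the later of last dose plus 30 days or Visit 5. Period 2 takes medications that started in or ran into it, "but not after the date of the last dose of study drug plus 30 days or Visit 9 whichever comes later". By contrast, the C-SSRS (SAP 10.5.2) is shown for each treatment period, overall, and separately for follow-up.

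Both periods are planned at 12 weeks (SAP 2.3). Only subjects who complete Period 1 enter Period 2 (SAP 2.2), and Safety Population 2 requires a dose in Period 2 (SAP 4.0). SAP 2.4 assumes 15% discontinuation in Period 1, so about 200 of 235 continue. It states a precision of about ±3% to 5% for AEs in Day 1 to Week 12 or in Weeks 12 to 24. SAP 10.2 plans no exposure-adjusted rates.

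**The concern.** The primary objective is the safety of concomitant use, and its main output is the set of AE tables by period. Protocol 4.2 marks the choice of control group as not applicable. A reader of the report will therefore set the Period 2 column beside the Period 1 column to judge whether adding ubrogepant changed the AE profile.

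That reading requires the two columns to cover similar time in similar subjects. Under one plausible reading of SAP 10.2.1, every subject who reaches Period 2 contributes a post-treatment tail to that column, while a Period 1 completer contributes none to the other. This alone would raise the Period 2 percentages. Loss of Period 1 dropouts changes who is counted and, if dropouts had more AEs than those who continued, would lower them. Because the assignment rule is missing, two programmers could follow the SAP correctly and produce different Period 2 tables.

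**Working it through.** **1. The plan's own figures.** Continuers: 235 × (1 − 0.15) = 199.75, about 200 as stated. Precision: half-width = 1.96 × √(p(1 − p)/n). With n = 200, 3% corresponds to p = 4.9% and 5% to p = 15.4%. With n = 235, the corresponding rates are 5.8% and 18.8%. The stated ±3% to 5% therefore reproduces for AE rates of roughly 5% to 15–19%.

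**2. Window for a completer.** Period 1: 12 × 7 = 84 days. Period 2 with the tail: 84 + 30 = 114 days, and 114/84 = 1.36. It ends about four weeks after Week 24, beyond the Weeks 12 to 24 span to which the stated precision refers.

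**3. Effect on a crude percentage.** Assume a constant hazard that continues unchanged after the last dose. The 114-day risk is then 1 − (1 − p)^(114/84).

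| 84-day risk p | 114-day risk | Shift, points | 95% half-width at p, n = 200 |
|---|---|---|---|
| 5% | 6.7% | 1.7 | 3.0 |
| 10% | 13.3% | 3.3 | 4.2 |
| 20% | 26.1% | 6.1 | 5.5 |
| 50% | 61.0% | 11.0 | 6.9 |

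**4. Allowing for dropout.** Assume dropout times uniform over each period (mean 42 days) and a 30-day tail for each dropout. Take the plan's 15% for Period 1. Period 2 dropout is not in the documents, so 0% to 15% is assumed.
- Period 1 mean window: 0.85 × 84 + 0.15 × (42 + 30) = 82.2 days.
- Period 2 mean window with the tail: 114 days at 0% dropout; 0.85 × 114 + 0.15 × 72 = 107.7 days at 15%.
- Ratio: 107.7/82.2 = 1.31 to 114/82.2 = 1.39.
- For an 84-day risk of 10%, the crude percentages are 9.8% in Period 1 and 12.6–13.3% in Period 2. For 20%, they are 19.6% and 24.8–26.1%.

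**5. If the tail is not counted in Period 2.** The Period 2 mean window is 84 days at 0% dropout, or 0.85 × 84 + 0.15 × 42 = 77.7 days at 15%. Against 82.2 days in Period 1, the ratio is 0.95 to 1.02. If Period 1 dropouts also lose their tail, Period 1 is 77.7 days and the ratio is 1.00 to 1.08.

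**6. Selection.** If the Period 1 AE rate is r in all 235 and q in the 35 who drop out, the rate in the 200 who continue is (235r − 35q)/200. The documents give neither r nor q, so no size follows from them.

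**The case against.** The strongest reply is that SAP 10.2.1 never places post-treatment events in Period 2. The rule cited in support governs medications, not AEs, and closes at a different point. That stands, so the 114-day window is conditional.

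A reader might go further and infer that Period 2 covers 114 days while Period 1 covers 84 days in every subject. The documents do not support this. The assignment is unstated, and the assumed 15% dropout shortens Period 1 treatment to a mean of 77.7 days under uniform dropout times. Dropouts may also carry their own 30-day tail.

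A reader might also infer that Period 1 is the only internal reference and that the planned outputs reveal nothing about either effect. That is too strong:
- SAP 10.6 summarises TEAEs by ubrogepant use, including subjects who never used it.
- The newly emergent table limits how much the tail can contribute.
- Discontinuations with reasons, AEs leading to discontinuation, atogepant duration by period and subject-level AE listings are all planned.
- Kaplan-Meier curves are planned for a few named AEs, although over the whole open-label period.

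These outputs give partial information. None gives a Period 2 percentage over a stated window, or a Period 1 percentage in the subjects who continued.

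It is also true that no between-period test is planned, that the sample size targets precision within each period, and that constant hazard is an assumption. If AEs cluster soon after first dose or fall once drug stops, the tail adds less than the table shows. These points lower the weight of the concern but do not supply the missing rule.

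**Conclusion.** The concern holds in conditional form. SAP 10.2.1 leaves open which period receives post-treatment TEAEs.

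If Period 2 receives them, its mean window is about 1.31 to 1.39 times that of Period 1. A 10% risk then reads as about 13% and a 20% risk as about 26% with no change in hazard. These shifts are about as large as the planned ±3% to 5%. They rest on constant hazard continuing after the last dose, uniform dropout times, and an assumed Period 2 dropout of 0–15%. If Period 2 does not receive them, the window imbalance is negligible.

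In both cases the Period 2 column contains Period 1 completers only, so the two percentages describe different subjects. The documents do not allow that effect to be sized, and a net direction of bias cannot be claimed. The issue concerns side-by-side interpretation of descriptive tables; no planned test is affected. This is a cheap improvement.

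**What to change.** In SAP 10.2.1:

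1. State that each period column counts AEs with onset from the start of that period to the last dose or, for Period 1 subjects who continue, to the start of Period 2. Show TEAEs after the last dose, from both periods, in a separate follow-up column, and keep them in the overall total. The existing newly emergent table can serve as that column.
2. Add exposure-adjusted incidence for each period beside the crude percentages, with a note that it assumes a roughly constant hazard and so does not fully equalise the periods for early-onset AEs.
3. Repeat the Period 1 TEAE summary in Safety Population 2, so that both periods can be read in the same subjects.

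The cost is SAP wording and a few extra table columns from data already collected. The on-treatment Period 2 percentage will be slightly lower than one that includes the tail, which is why the follow-up column should stand beside it.
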